### 7.5.2.3 Analyses of HRCT

Values of HRCT variables described in [Section 3.4.3](#) will be summarized with descriptive statistics by treatment arm and visit for the ITT Population. The summary will include the change from baseline to Visit 14 (or ET) for each parameter. Results from unscheduled visits will not be included in summary tables or statistical models, but will be included in subject-level listings. In addition, subjects who have visit 14 assessment and subjects who withdraw from treatment before visit 14 and have only ET assessment will be summarized separately for each HRCT variable.

The qualitative overall change in ILD from baseline to Visit 14/ET will be analyzed using the Kruskal-Wallis (KW) test. The test statistic and p-value from the KW test will be reported along with the pairwise comparisons of each active treatment arm with placebo.

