## Statistical Analysis Plan

Sponsor Name: Nitto Denko Corporation  
Sponsor Protocol ID: ND-L02-s0201-005

- ND-L02-s0201 for Injection low dose (45 mg)
- Placebo.

The randomization via the interactive web response system (IWRS) will be stratified by the receipt of standard of care at the enrollment of the study, defined as administration of either nintedanib or pirfenidone, or no standard of care. As there is no minimum number of subjects for a given strata of standard of care, balance in strata across the 3 treatment arms is required.

Eligible subjects who meet the inclusion criteria and do not meet any of the exclusion criteria and have provided informed consent will be enrolled in the study. Subjects will participate in the study for approximately 40 weeks consisting of a Screening and Baseline period of up to 6 weeks, a treatment period of 24 weeks including a total of 12 doses and an End-of-Treatment visit 2 weeks after the final dose (Visit 14), and a follow-up visit 4 and 10 weeks after Visit 14, or until they withdraw from the study or the study is terminated by the Sponsor. During the treatment period ND-L02-s0201 for Injection will be administered by intravenous (IV) infusion Q2W ( $\pm$  4 days for Visit 3 or  $\pm$  7 days for Visits 4 to 13, ensuring a minimum of 7 days between each dose) for a total of 12 doses. Subjects may be premedicated to mitigate the risk of infusion-related reactions at the discretion of the Investigator.

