**Statistical Analysis Plan**

Sponsor Name: Nitto Denko Corporation  
Sponsor Protocol ID: ND-L02-s0201-005

[REDACTED]

Possible values (as %) for each region will include "Absent", "1-25", "26-50", "51-75", and "76-100". Results for unreadable scans will be reported as "Unknown".

The central reader's assessment of overall change in interstitial lung disease (ILD) from baseline to Visit 14 (or ET) will have possible values of "Much Better", "Better", "Same", "Worse", "Much Worse", or "Unknown".

[REDACTED]

[REDACTED]

	[REDACTED]					
[REDACTED]						
[REDACTED]						
[REDACTED]						
[REDACTED]						
[REDACTED]						

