### 7.5.2.4 Analysis of Time to First IPF Exacerbation or Death

Time to first IPF exacerbation or death is defined as the time from start of study treatment to first acute exacerbation of IPF which is determined by the investigator (Adverse event CRF, AE preferred term equal to Idiopathic pulmonary fibrosis) or death for each subject. Subjects who do not experience acute exacerbation of IPF will be censored to the last known alive date.

The analysis of time to first IPF exacerbation or death of each active treatment arm versus placebo will be performed using a log-rank test stratified with standard of care to generate p-value for each comparison. Median time to first IPF exacerbation and corresponding 95% CI as well as proportion of subjects without the event at 8-week interval will be summarized for each treatment arm using the Kaplan-Meier (KM) analysis. KM plot of time to first IPF exacerbation will also be presented by treatment. In addition, the hazard ratio and 95% CI will be calculated from a stratified Cox proportional hazards model that includes standard of care as the strata.

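### The rank test of overall ILD change leaves out standard of care, the randomisation stratum; a stratified version is a free improvement

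*SAP*

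**What the plan says.** SAP 7.5.2.3 (Analyses of HRCT) gives the test in one sentence: "The qualitative overall change in ILD from baseline to Visit 14/ET will be analyzed using the Kruskal-Wallis (KW) test". The result is to be "reported along with the pairwise comparisons of each active treatment arm with placebo". The pairwise test is not named, and no stratum or covariate is mentioned for either step.

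SAP 2.2 says that randomisation is "stratified by the receipt of standard of care at the enrollment of the study" and asks for balance of the strata across the three arms. Other efficacy analyses use this factor:
- The QLF random coefficients model, also in SAP 7.5.2.3, has background standard of care as a fixed effect.
- SAP 7.5.2.4 uses a "log-rank test stratified with standard of care" and a Cox model stratified in the same way. SAP 7.5.2.5 repeats both for its time-to-event endpoints.
- The sensitivity ANCOVA in SAP 7.5.3 has standard of care as a covariate.

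On the outcome scale, SAP 3.4.3.1 says the central reader's "assessment of overall change in interstitial lung disease (ILD) from baseline to Visit 14 (or ET) will have possible values of" five ordered grades, from much better to much worse, plus *Unknown*. Just before that, the same section uses *Unknown* as the code for unreadable scans in the regional scores. SAP 6.2 says missing HRCT values at Visit 14 are not imputed; it does not mention *Unknown*.

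**The concern.** Stratified randomisation makes the arms alike in standard of care. The difference in mean ranks between arms then varies less from trial to trial than simple random allocation would imply. An unstratified rank test still uses the full variance of the pooled ranks, including the part between strata. If standard of care is related to ILD change, that variance is too large for the design: the true error rate falls below 5% and some power is given up. If it is unrelated, nothing is lost.

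At stake is the efficiency of the only named test of the central reader's overall ILD assessment, which is the qualitative part of the HRCT secondary endpoint. The error rate is not inflated.

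**Working it through.** **The plan's own figure.** There is none to reproduce. SAP 2.3 gives about 120 subjects, about 40 per arm, with no power, effect size or category distribution. The test level is 0.05 two-sided without multiplicity adjustment (SAP 7.1).

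**Tests compared.** The planned test is Kruskal-Wallis on the pooled ranks. For the stratified test, in each stratum *s* with *n* subjects, the score is r = midrank/(n + 1). For each arm but one, T sums over strata the arm's observed score total minus its expected total (arm size × stratum mean score). V = Σ n·v·(diag(p) − pp′), where v is the stratum variance of r and p holds the arm proportions. Q = T′V⁻¹T is referred to chi-squared with (number of arms − 1) degrees of freedom. With two arms this is the van Elteren test.

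**Assumptions not in the documents.** Placebo distribution 2/13/50/30/5% from much better to much worse; proportional odds; treatment log-odds −0.6 (45 mg) and −1.2 (90 mg); three strata of 13/13/14 per arm; a prognostic effect of standard of care spread evenly over the strata. 4000 simulated trials per setting, so the standard error is about 0.6 points near 79% power (√(0.79 × 0.21/4000) = 0.0064). A latent logistic SD is π/√3 = 1.81, which converts log-odds to SD units.

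| Log-odds range across strata (SD) | 90 mg vs placebo: KW / stratified | Loss, points | Three-arm: KW / stratified | Loss, points | Null error, pairwise KW |
|---|---|---|---|---|---|
| 0 | 79.2% / 78.9% | −0.3 | 70.4% / 70.0% | −0.4 | 4.6% |
| 0.5 (0.28) | 79.2% / 79.2% | 0.0 | 70.1% / 70.4% | 0.3 | 5.0% |
| 1.0 (0.55) | 78.4% / 79.6% | 1.2 | 68.0% / 70.0% | 2.0 | 4.2% |
| 1.5 (0.83) | 76.1% / 79.5% | 3.4 | 65.7% / 70.6% | 4.9 | 3.6% |
| 2.0 (1.10) | 73.9% / 79.2% | 5.3 | 61.3% / 70.4% | 9.1 | 2.8% |
| 3.0 (1.65) | 65.8% / 80.0% | 14.2 | 50.0% / 70.4% | 20.4 | 1.5% |

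The stratified tests kept a null error rate of 4.0% to 5.2% throughout. With strata of 18/16/6 per arm the losses are smaller: at range 2.0, 4.0 points pairwise (75.5% vs 79.5%) and 6.4 three-arm (64.3% vs 70.7%); at range 3.0, 11.0 (68.3% vs 79.3%) and 14.7 (54.9% vs 69.6%).

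**Rough check of the error rate.** At range 3.0 with three equal strata at −1.5, 0 and 1.5, the between-stratum variance is 1.5² × 2/3 = 1.50 and the within-stratum variance is π²/3 = 3.29. The ratio of true to assumed variance is 3.29/4.79 = 0.687, so the effective critical value is 1.96/√0.687 = 2.365, a two-sided error of 1.8%. The simulation gave 1.5%.

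**A second simulation** used a latent effect of 0.6 SD and strata of 10/15/15 per arm. Unstratified versus stratified power was 67.7% vs 67.3% with no standard-of-care effect, 66.9% vs 69.9% with 0.4 SD per level, and 54.7% vs 67.5% with 0.8 SD per level, which is a 1.6 SD spread over three strata.

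**Both antifibrotics shifted equally from none** (same design, other assumed cut-points): 68% vs 68% at 0.4 SD, 68% vs 70% at 0.6 SD and 65% vs 69% at 0.8 SD, with unstratified null error about 4.3%.

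**The case against.** The strongest reply is that nothing in the documents shows standard of care to be prognostic for reader-rated ILD change. A reader might infer that the planned test does lose power, or that its error rate is below 5%. Neither follows: both depend on an assumed effect, and both vanish without one. A loss above 10 points needs strata about 1.6 SD apart, more than 2.5 times the 0.6 SD drug effect assumed in the second simulation. If the two antifibrotics act alike relative to none, the loss is about 0 to 4 points. This stands, and it limits the size of the point.

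It is also fair that Kruskal-Wallis is not a lone exception. The chi-squared comparisons of event rates in SAP 7.5.2.4 and 7.5.2.5 name no stratum either. Those endpoints do have stratified time-to-event analyses beside them; the overall ILD reading has no such companion.

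SAP 7.5.4 plans subgroup analyses of the secondary endpoints by standard of care. These give results within each stratum, in smaller groups, and descriptive only where there are fewer than 10 subjects across the two arms compared. They do not replace one combined stratified test.

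Finally, a reader might infer that *Unknown* is part of the ranked scale, perhaps as the worst grade. The documents do not say so. It is listed as a possible value and used as a code for unreadable scans; nothing says it is ranked, parts of SAP 3.4.3.1 are redacted, and SAP Appendix 4 refers to a review charter that may hold the rule. Only the lack of a visible sentence can be noted. It is still worth adding one. Under the assumptions above, with a standard-of-care range of 0.5 and 10% *Unknown*, pairwise power is 75.2% if these readings are excluded and 58.6% if they are ranked beyond much worse. With no treatment effect and *Unknown* in 5% of placebo and 15% of active subjects, the false-positive rate is 4.5% if excluded and 12.5% if ranked.

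**Conclusion.** The point holds as a minor one. The planned test and its pairwise comparisons omit the randomisation stratum that the QLF, log-rank, Cox and sensitivity ANCOVA analyses account for, and no reason is given. The test is valid and at worst conservative.

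Under the assumed effects the loss is nil with no relation and at most about 5 points up to a spread of roughly 0.8 SD across strata. At about 1.1 SD it is 4 to 5 points pairwise and 6 to 9 for the three-arm test. It exceeds 10 points only for very large differences, around 1.6 SD. These figures rest on assumed category distributions, stratum sizes and treatment effects; SAP 2.2 sets no minimum stratum size. They also assume three strata, and the wording of SAP 2.2 could also be read as two (any antifibrotic or none).

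Stratifying is worth doing despite the uncertain gain, because it cost no more than simulation error when the factor was irrelevant. Priority is low: this is one secondary endpoint in a Phase 2 trial with safety as primary endpoint, no primary efficacy endpoint and no multiplicity control.

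**What to change.** In SAP 7.5.2.3:
- Replace the three-arm Kruskal-Wallis test by the CMH row-mean-scores test with modified ridit scores, stratified by standard of care as randomised. This keeps the planned overall comparison.
- Name the van Elteren test, with the same strata, for each dose versus placebo. This also settles which pairwise test is meant.
- State the stratum levels as implemented in the IWRS.
- As a clarification, state that *Unknown* is treated as missing and not ranked, and report its count by arm. If the review charter already says this, a cross-reference is enough.

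The cost is two or three sentences and a standard procedure call, with no new data and no change to sample size or conduct. It should be made before unblinding.

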## Statistical Analysis Plan

Sponsor Name: Nitto Denko Corporation  
Sponsor Protocol ID: ND-L02-s0201-005

A random coefficients model will be used to analyze the rate of change in the quantitative QLF score from baseline to Visit 14 as well as the absolute change from baseline at Visit 14. The model will include QLF score as the dependent variable, background standard of care, treatment, time and the interaction of treatment\*time and baseline QLF score as fixed effects, and subject and subject\*time as random effects. Subjects with missing values at Visit 14 will not be imputed for the analysis. The unstructured covariance model (UN) will be used to estimate the variance and covariance of random slopes and intercepts. If the computational algorithm fails to converge, the variance components (VC) covariance structure will be used for the analysis.

Reporting of model results will include the estimated mean change from baseline, adjusted for baseline QLF and standard of care, at Visit 14 with corresponding 95% CIs for each treatment arm. In addition, mean slope (rate of change) of QLF from baseline to Visit 14 for each treatment arm will be estimated along with 95% CIs. Treatment differences between mean slope and corresponding p-values will be presented. No adjustments for multiple comparisons will be made. The analysis will be repeated for subjects who have visit 14 assessment and subjects who withdraw from treatment before visit 14 and have only ET assessment. Spaghetti plots of individual QLF data over time will be produced for each treatment arm with estimated means from the random coefficient model and 95% CIs at Visit 14 superimposed.

Similar analysis will be repeated for relative change of QLF from baseline (derived as  $100 * (\text{QLF score at Visit 14} / \text{ET-Baseline QLF score}) / \text{Baseline QLF score}$ ).

Other quantitative HRCT variables including ground glass opacity, reticulation, honeycombing, normal lung, and emphysema will be analyzed similarly as QLF score.

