### 6.2 Handling of Dropouts, Missing Data, and Outliers

Missing values on FVC, DLCO and DLCO corrected for hemoglobin, HRCT analysis variables, [REDACTED] at Visit 14 (Day 169) will not be imputed. In situations where the efficacy endpoints are missing, all available data will be analyzed with a mixed-effects model for repeated measures (MMRM). To evaluate robustness of results, sensitivity analyses will be performed by imputing missing data using statistical modelling of available data.

Incomplete dates (partial or missing dates) for start date of AEs will be imputed and used to determine treatment-emergent status as follows:

- If the start date of an AE is completely missing, the first dosing date (Day 1) and time will be used for the imputation and the AE will be considered treatment-emergent.
- If the start date of an AE is missing day and month:
  - If the year of the AE start date is the year of the first dosing date, the month and day will be imputed using the month and day of first dosing date;
  - Otherwise, the month and day will be imputed as January 1.
- If the start date of an AE is missing the day only:

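### With two HRCT scans per subject, the SAP's random-coefficients model for QLF can have no likelihood maximum, and its change from baseline is not adjusted as promised

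*SAP*

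**What the plan says.** SAP 7.5.2.3: "A random coefficients model will be used to analyze the rate of change in the quantitative QLF score from baseline to Visit 14". The response is the QLF score itself. The fixed effects are standard of care (SOC), treatment, time, treatment-by-time and baseline QLF. Intercept and slope are random, with unstructured (UN) covariance and a fallback: "If the computational algorithm fails to converge, the variance components (VC) covariance structure will be used for the analysis". The promised output is as follows: "Reporting of model results will include the estimated mean change from baseline, adjusted for baseline QLF and standard of care". The model is then extended twice: "Similar analysis will be repeated for relative change of QLF from baseline", and "Other quantitative HRCT variables including ground glass opacity, reticulation, honeycombing, normal lung, and emphysema will be analyzed similarly as QLF score".

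On the number of scans, 7.5.2.3 says: "The summary will include the change from baseline to Visit 14 (or ET) for each parameter". SAP 3.2 and 3.4.3.1 and protocol 13.1.2.1 use the same two time points, and protocol 8.1 refers to a single screening HRCT at Visit 1b. The HRCT timing text (protocol 11.2.3.1) is redacted. Section 7.5.2.3 defines neither the time variable nor whether baseline is a response row.

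SAP 6.2 covers the HRCT variables and names a different model: "In situations where the efficacy endpoints are missing, all available data will be analyzed with a mixed-effects model for repeated measures (MMRM". SAP Section 8 says that a random coefficient model replaces ANCOVA in 7.5.2.3.

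**The concern.** Two scans give one change per subject. A slope starting at baseline can then be estimated only if the baseline scan is a response row, yet baseline QLF is already a covariate. Using one number in both places breaks the likelihood whenever baseline time is constant. Separately, baseline and SOC enter without time interactions, so they drop out of any within-subject change.

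HRCT change is a stated secondary objective, and five other quantitative variables inherit the model. The programmer could meet a model that will not converge, with a fallback that fails for the same reason, or could report as adjusted a difference that is not.

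**Working it through.** The plan gives no QLF standard deviation, effect size or power, so there is no figure to reproduce.

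**Inputs.** From the SAP: about 120 subjects, 40 per arm (2.3); three SOC levels (7.4); the model terms (7.5.2.3); nominal scan times 0 and 24 weeks. Assumed for illustration: baseline mean 20 and SD 10, residual SD of change 4, regression of change on baseline -0.1. Steps 1 and 3 do not depend on these values.

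**Step 1: is there a maximum?** For subject *i* with baseline *b*:

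y(t) = μ + SOC + τ(arm) + β·b + [γ + δ(arm)]·t + u0 + u1·t + e, with y(0) = b.

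Set β = 1 and μ, SOC and τ to 0. Every baseline row then has residual 0. Its variance is v = Var(u0) + Var(e). Let both parts shrink and keep Var(u1) above 0. The baseline rows contribute -(n/2)·ln v, which grows without limit, while the follow-up rows stay finite. REML uses n - 6, because six coefficients (intercept, two SOC, two treatment, baseline) are spent on these rows. Gain per tenfold fall:

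- ML: 120/2 × ln 10 = 138.2
- REML: (120 - 6)/2 × ln 10 = 131.2

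REML log-likelihood with the intercept and residual variances both set to the value shown:

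| Variance | 1 | 0.1 | 0.01 | 0.001 | 0.0001 | 0.00001 |
|---|---|---|---|---|---|---|
| UN | -499.5 | -368.0 | -236.8 | -105.6 | 25.6 | 156.9 |
| VC | -499.4 | -368.0 | -236.7 | -105.5 | 25.8 | 157.0 |

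A standard mixed-model routine (UN) failed to converge under both ML and REML.

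**Step 2: which codings share the fault?** Log-likelihood along the same VC path, variance from 10 down to 0.00001:

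- Days counted from the baseline scan: -640.1 rising to 202.6. No maximum.
- 20% of subjects with baseline only: -568.5 rising to 267.1. No maximum.
- 20% with an ET scan at its own time: -631.7 rising to 182.2. No maximum.
- Days counted from Day 1: peaks near -436.0, then falls steeply. Baseline times now differ, so an exact fit at baseline would need zero slope variance.
- A third scan: peaks near -763.2, then falls. The residual variance can no longer vanish.
- Six of 120 subjects with both ET and Visit 14 scans: peaks near -431.0, then falls, for the same reason.

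Day-1 coding was examined further in 40 simulated data sets with an assumed 15% ET. VC had a finite maximum in all 40, with residual variance below 0.001 in each. UN was singular in 38. In 60 more data sets the VC slope contrast equalled the unadjusted difference in change per scan interval.

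**Step 3: is the change adjusted?** The expected value of y(24) - y(0) is 24·[γ + δ(arm)]; β·b and SOC cancel. With complete nominal-time data the model's changes equalled the raw arm means at every covariance matrix tried: 1.4410 (placebo), 0.6281 (45 mg) and 0.6870 (90 mg). Differences from placebo:

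- Model: 0.6281 - 1.4410 = -0.813; 0.6870 - 1.4410 = -0.754
- ANCOVA on baseline, SOC and arm: -0.773; -0.773

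**Step 4: cost in precision.** The standard error of the raw change relative to ANCOVA is √[1 + (1 - s)²·(SDb/SDe)²], where s is the regression of the Visit 14 value on baseline, SDb the baseline SD and SDe the residual SD.

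- SD ratio 2: √1.04 = 1.020 (s = 0.9); √1.16 = 1.077 (s = 0.8)
- SD ratio 1: 0.5% to 2.0% larger over the same slopes
- SD ratio 3: 4.4% to 16.6% larger

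This is an average. In the single data set above the raw standard error was 0.883, against 0.888 and 0.894 for ANCOVA.

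**Step 5: baseline not a response row.** At one nominal time the nine fixed-effect columns have rank 6: time is aliased with the intercept, and treatment-by-time with treatment. No slope can be estimated, although the Visit 14 contrast is then the ANCOVA one.

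**Step 6: relative change.** The SAP formula defines it only at follow-up, so step 5 applies. Adding a baseline row of zeros, in a second simulated data set, gives VC REML values of -796.4, -665.2, -534.0 and -402.7 at baseline-row variance 10, 1, 0.1 and 0.01: again no maximum.

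**Step 7: candidate repairs.** Only removing the baseline covariate is not enough: the UN log-likelihood is -762.7101 at residual variances 0.1, 1, 3 and 6, so that variance is not identified. A two-visit model with one unstructured 2×2 matrix, run with 18 of 120 follow-up scans missing, gave contrasts of -2.634 and -1.485, equal to ANCOVA to four decimals.

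**The case against.** The strongest reply is that the failure depends on details the public text does not settle. The HRCT schedule is redacted, and a third scan would remove the problem. SAP 6.1 assigns records to nominal visits but does not define a model's time variable, and it also defines study days from Day 1, the coding under which a maximum exists. The reference to "subjects who withdraw from treatment before visit 14 and have only ET assessment" leaves room for subjects with both an ET and a Visit 14 scan, and a few of those bound the likelihood. All this stands. A reader might infer that the SAP's own visit rule makes the analysis impossible, or that any two-scan coding fails; the documents support neither.

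A reader might also infer from SAP 6.2 that the choice between MMRM and random coefficients is open until after unblinding. Section 8 names the model for 7.5.2.3, and protocol Section 13 requires the SAP to be final before unblinded analysis. The mismatch is real but secondary.

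Finally, HRCT also has descriptive summaries, a Kruskal-Wallis test and an ANCOVA after multiple imputation (7.5.3), and moving to ANCOVA reverses a documented decision. That limits the damage. It does not repair a main model whose slope and adjusted change conflict on the likely two-scan reading.

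**Conclusion.** Wrong as written, at lower severity, for a secondary endpoint only. With two scans and a baseline time common to all subjects, the model has no likelihood maximum under UN or VC. With complete nominal-time data its treatment contrast in change is the raw difference. Leaving baseline out of the response rows restores baseline adjustment of the Visit 14 mean but removes the slope.

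This rests on two scans, which is inferred, and on baseline being a response row, which a two-scan slope requires but the SAP does not state. It should not be read as bias: the contrast stays unbiased, and the loss of precision is modest for most values tried, on assumed SDs and slopes. The primary safety objective is unaffected.

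**What to change.** Before unblinding, amend 7.5.2.3 for QLF and the other quantitative HRCT variables:

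- **Main analysis:** ANCOVA of change to Visit 14 on treatment, baseline value and SOC, the covariates already in 7.5.3. Use ANCOVA for relative change too.
- **Alternative that keeps baseline-only subjects, as Section 8 intends:** a two-visit model with unstructured 2×2 covariance, common baseline mean, treatment-by-visit and SOC-by-visit terms, and no baseline covariate.
- **ET-only scans:** analyse them in the separate repeat already planned, not as Week 24 values in the main model.
- **If a rate is wanted:** each subject's change divided by the actual scan interval, adjusted for baseline and SOC.
- **If the redacted schedule has a further scan:** define the time variable, and use baseline as a response or a covariate, not both.
- **Consistency:** align the MMRM sentence in 6.2 and the entry in Section 8 with the chosen model.

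The cost is SAP wording and simpler programming, with no new data. The model-based slope is lost, and ANCOVA drops subjects without a Visit 14 scan from the main model.

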## 8. SELECTION AND WITHDRAWAL OF SUBJECTS

### 8.1. Inclusion Criteria

To be randomized, all subjects must meet the criteria listed below.

1. Males and females between 40 and 80 years of age, inclusive, at the time of consent.
2. Diagnosis of IPF within 5 years before Visit 1a, confirmed by the **Principal** Investigator (PI) using American Thoracic Society (ATS)/European Respiratory Society (ERS)/Japanese Respiratory Society (JRS)/Latin American Thoracic Association (ALAT) guidelines (Raghu et al, 2011 or Raghu et al, 2018; see Section 11.2.5).
  - a. Clinical management of the patient at the site must be for IPF and the PI must be convinced that all locally available information support UIP/IPF is the most likely diagnosis. It is mandatory that the PI consider overreader interpretation of Visit 1b HRCT and, if performed, SLB in order to determine that a subject is eligible for this trial.
3. Extent of fibrosis greater than emphysema on HRCT.
4. If on pirfenidone or nintedanib, unchanged dose for at least 12 weeks before Visit 1a. Subjects may not be on both pirfenidone and nintedanib.
5. Forced vital capacity (FVC)  $\geq$  45% of predicted.
6. Diffusion capacity of the lung for carbon monoxide (DLco) corrected for hemoglobin  $\geq$  30% of predicted value.
7. Pulse oximetry saturation  $\geq$  90%, at rest while breathing ambient air or  $\leq$  2 L/minute supplemental oxygen by nasal prongs/cannula (see Section 11.2.1).
8. Ratio of forced expiratory volume in 1 second (FEV1) to FVC  $\geq$  0.70.
9. Adequate liver and renal function, as demonstrated by:
  - Total bilirubin  $\leq$  1.5  $\times$  upper limit of normal (ULN), unless participant has a documented history of Gilbert's syndrome
  - Aspartate transaminase (AST) and alanine transaminase (ALT)  $<$  2.5  $\times$  ULN
  - Creatinine  $<$  2  $\times$  ULN
  - Serum albumin  $>$  3.5 g/dL
10. Life expectancy of  $\geq$  12 months.  
[REDACTED]
12. Women of childbearing potential (WCBP) must be willing to use a highly effective method of contraception throughout the study and study follow up or for at least 90 days after the last dose of study treatment (refer to Section 10.3.2.3).
13. Women must be willing not to breastfeed for 90 days after the last dose of the study treatment.

14. Males must agree to use a condom throughout the study and for 90 days after the last dose of study treatment to prevent seminal transmission of the investigational product (IP).

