#### **11.2.5. Diagnosis of Idiopathic Pulmonary Fibrosis**

The diagnosis of IPF will be confirmed by the PI using ATS/ERS/JRS/ALAT consensus criteria (Raghu et al, 2011 or Raghu et al, 2018).

Clinical management of the patient at the site must be for IPF and the PI must be convinced that all locally available information support that UIP/IPF is the most likely diagnosis. It is mandatory that the PI consider overreader interpretation of Visit 1b HRCT and, if performed, SLB in order to determine that a subject is eligible for this trial.

The diagnosis of IPF may be made on the basis of HRCT and, when performed, SLB patterns in accordance with respective tables in the guidelines. Additional clinical data may also be used. In accordance with local implementation of the guidelines the diagnosis of IPF may also be established by review of the case at multidisciplinary discussion (MDD).

Documentation of the diagnosis must be included in the subject's source records.

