### 7.5.3 Sensitivity Analysis

- **Multiple imputation assuming missing not at random (MNAR)**

Sensitivity analysis will be performed for secondary efficacy endpoints including change and percent change from baseline in FVC (L) and percent predicted FVC (%), change from baseline in DLco corrected for hemoglobin and DLco not corrected for hemoglobin, and change and percent change from baseline in quantitative HRCT variables using multiple imputations with missing data imputed prior to fitting the linear regression. An assumption of MNAR will be made based upon an approach using regression based multiple imputations with missing data for all subjects imputed from a regression model estimated from patients in the placebo arm who stay on until visit 14. SAS PROC MI and MIANALYZE will be used to generate 100 complete datasets and combine the results from each complete dataset analyzed using ANCOVA model with baseline value, treatment arm, and standard of care as covariates.

- **Excluding subjects with deviations**

All the secondary efficacy analysis described in section 7.5.2 will be repeated using the PP population.

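### Percent change from baseline is planned for HRCT features (honeycombing, emphysema, possibly ground glass opacity) whose baseline nothing visible keeps above zero

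*SAP*

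**What the plan says.** SAP 7.5.2.3 fits a random coefficients model to the QLF score for its slope and its absolute change at Visit 14. It then adds a second outcome: "Similar analysis will be repeated for relative change of QLF from baseline". The printed formula is garbled by a slash, but the evident meaning is 100 × (Visit 14 or ET value − baseline) / baseline. The next sentence extends the approach: "Other quantitative HRCT variables including ground glass opacity, reticulation, honeycombing, normal lung, and emphysema will be analyzed similarly as QLF score".

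The word *similarly* could be read as covering the absolute analysis only. SAP 7.5.3 makes that unlikely, because its missing-not-at-random analysis lists "change and percent change from baseline in quantitative HRCT variables using multiple imputations". The same sentence lists DLco with change only, so naming percent change for HRCT looks deliberate.

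On baseline values, Protocol 8.1 inclusion criterion 3 reads "Extent of fibrosis greater than emphysema on HRCT". On diagnosis, Protocol 11.2.5 says "The diagnosis of IPF may be made on the basis of HRCT and, when performed, SLB patterns", and it also allows other clinical data and multidisciplinary discussion to be used.

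On missing data, SAP 7.5.2.3 says "Subjects with missing values at Visit 14 will not be imputed for the analysis". SAP 6.2 likewise deals with missing Visit 14 values. Neither addresses a ratio that cannot be formed although both scans were read.

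**The concern.** A ratio to baseline is a usable scale only when baseline is well above zero for nearly everyone. Criterion 3 bounds emphysema from above only, so a subject with none is eligible. No minimum extent of honeycombing or of ground glass opacity is visible.

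Three things are at stake in the percent-change results:

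- A subject with a baseline of 0 has no percent change, and the visible SAP does not say what happens to that subject.
- A few subjects with near-zero baselines can set the arm mean, the confidence interval and the p-value through clinically trivial absolute changes.
- In the 7.5.3 analysis, an undefined value could be coded as missing and replaced by a prediction from placebo completers, although the subject's scans were observed.

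**Working it through.** The documents give no effect size, SD or baseline distribution for any HRCT variable, so there is no plan figure to reproduce. The only inputs taken from the plan are the relative-change formula (SAP 7.5.2.3) and about 40 subjects per arm (SAP 2.3). Everything else below is an assumption. Points means units of the score; its true unit is not visible.

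**1. The formula at different baselines, for a 1-point rise: 100 × 1 / baseline**

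| Baseline | Percent change |
|---|---|
| 10 | +10% |
| 5 | +20% |
| 1 | +100% |
| 0.5 | +200% |
| 0.1 | +1000% |
| 0 | undefined |

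**2. Leverage of one subject.** At a baseline of 0.1, that subject contributes 1000 / 40 = 25 percentage points to the arm mean. On the absolute scale the contribution is 1 / 40 = 0.025 points.

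**3. Zero baselines, if those subjects were dropped.** Let q be the share of subjects with a baseline of 0 (assumed). The number without a value per arm is 40q, and the standard error rises by 1/√(1 − q). Power is shown for a reference difference of 0.64 SD, two-sided 0.05, normal approximation, with n = 40(1 − q) per arm: Φ(0.64 × √(n/2) − 1.96).

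| q | No value, per arm | SE factor | Power |
|---|---|---|---|
| 0 | 0 | 1.00 | 0.82 |
| 10% | 4 | 1.05 | 0.78 |
| 20% | 8 | 1.12 | 0.73 |
| 30% | 12 | 1.20 | 0.67 |
| 50% | 20 | 1.41 | 0.53 |

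**4. Near-zero baselines.** This is a simulation of 4000 trials with 40 per arm and a lognormal baseline. Absolute change has SD 1 point, with mean +0.5 in the comparator arm and a 0.7-point difference between arms. Scores are floored at 0, and a two-sided t-test is applied to each scale. The three middle columns describe the comparator arm (median over runs).

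| Baseline median (log-SD) | Share of total absolute percent change from top 3 of 40 | Arm mean | Arm median | Power, absolute change | Power, percent change |
|---|---|---|---|---|---|
| 15 (0.5), QLF-like | 25% | +4% | +3% | 0.87 | 0.80 |
| 2 (1.0) | 36% | +43% | +18% | 0.87 | 0.57 |
| 1 (1.5) | 52% | +164% | +26% | 0.84 | 0.28 |
| 0.5 (2.0) | 67% | +682% | +40% | 0.83 | 0.13 |

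The simulation uses a treatment effect that is the same absolute size at every baseline, which favours the absolute scale, so the power columns illustrate the problem and do not estimate it for this trial. The first row shows why relative change is tolerable for a score with a substantial baseline. The lower rows show how it fails as baseline approaches zero.

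**The case against.** The strongest reply is that little depends on these tables. The primary endpoints are safety, SAP 7.5.1 records that there is no primary efficacy endpoint, and no visible decision rule uses percent change in an HRCT sub-feature. The descriptive HRCT summaries in 7.5.2.3 and the HRCT forest plots in 7.5.4 name change from baseline, not percent change. All of this stands and keeps the point minor.

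The second reply is that the defining text is not visible. SAP 3.4.3.2, on the quantitative variables, is redacted, and Appendix 4 refers to an external review charter. The unit, any measurement floor and a convention for zero baselines could be there. This also stands: it cannot be asserted that no rule exists.

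The third reply is that zero baselines are not demonstrated. A reader might point to the reader scale in SAP 3.4.3.1 ("Possible values (as %) for each region will include"), whose lowest grade is absent. But that scale is qualitative and regional. A region graded absent does not show that the quantitative score is zero, so the scale is at most a hint that the plan expects regions without an abnormality.

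A reader might also infer that new honeycombing would go uncounted in this trial. The documents do not support that. The slope and absolute-change models in 7.5.2.3 have a defined value for a subject who starts at 0, and the central reader's overall change in ILD is tested separately. Nor do the documents say that zero-baseline subjects leave the percent-change analysis; they are silent on it.

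What survives is that the planned ratio can be undefined or unstable for these features, and the visible plan neither prevents nor handles it.

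**Conclusion.** The concern holds in a limited form. SAP 7.5.2.3 and 7.5.3 together plan percent change for all quantitative HRCT features, and for honeycombing, emphysema and possibly ground glass opacity nothing visible keeps the denominator away from zero. The arithmetic consequence is certain where such baselines occur: no value at 0, and a 25-percentage-point shift in a 40-subject arm mean from one subject rising from 0.1 to 1.1.

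How often they occur is unknown; the shares and distributions above are assumptions. Normal lung is unlikely to be near zero, QLF is less exposed, and there is no argument for a near-zero reticulation baseline in subjects enrolled for fibrosis. The damage is confined to the percent-change model and the percent-change multiple-imputation analysis. Severity is minor: these are sub-features of a secondary endpoint in a trial whose primary aim is safety.

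**What to change.** In SAP 7.5.2.3 and 7.5.3, before unblinding:

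- Analyse honeycombing, emphysema and ground glass opacity by slope and absolute change only. Keep relative change for QLF, reticulation and normal lung.
- Add a sentence such as: *A percent change that is undefined because the baseline value is 0 is not treated as missing and is not imputed in the multiple-imputation analysis.* This also covers a stray zero in the features that keep relative change.
- If SAP 3.4.3.2 or the review charter already gives a rule for zero or near-zero baselines, cite it in 7.5.2.3 and 7.5.3.
- Correct the printed relative-change formula so that it reads as a difference divided by baseline.

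The cost is a few lines of SAP text and the loss of a few secondary percent-change tables. No data collection changes, and the absolute-change results stay as planned.
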